Specifically, the ePOCT+ tool will guide clinicians on:

- i) Decision on immediate referral to a higher level facility
- ii) Medical history (questions to ask caregivers and/or children)
- iii) Physical exam (signs to look for)
- iv) POC diagnostic tests that should be performed in a given clinical context (**Table 2**)
- v) Diagnoses
- vi) Treatments (including medicines and supportive treatments)
- vii) Counseling (explanation of final diagnoses, treatments, and follow-up)

Biosensors (presently pulse oximeter and hemoglobinometer) and rapid tests (presently malaria, HIV, semi-quantitative CRP, and urine dipstick) used for the intervention will have to meet requirements for use at the PHC level, including adequate measurement accuracy, stability in high-temperature and dusty settings, and affordability. Once adequate biosensors and POC tests are identified, manufacturer negotiations are complete, devices are procured, and the regulatory framework is in place, they will be used by HWs upon recommendation provided by ePOCT+ (**Table 2**).

The ePOCT+ CDSA guides the clinician step-by-step through the consultation process. The algorithm is able to integrate all the information from the consultation and provide diagnostic classifications and related treatment recommendations. The application will be radically different from the existing software used in the clinical settings such as eIMCI. It will allow clinicians to freely navigate up and down the algorithm, adding or modifying clinical information of any type (exposures, symptoms, signs, lab test results) at any time, in order to follow the natural consultation process (rather than forcing a clinician to assess the patient condition in a fixed order). The interface will also be much more user-friendly, and allow integration of alerts of ongoing epidemics, definitions or translations of medical terms in local languages, explanations and illustrations (pictures, sound or video clips) of symptoms or signs that are difficult to assess and those that are specific to rare diseases, and educational information on why a certain disease is being considered or not considered in a particular patient. The application will be available in English and French, with the possibility of also translating the client-facing content into Kinyarwanda.

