2.1.2 Secondary outcomes

All secondary outcomes are compared between the intervention (ePOCT+) and control (routine care) arms.

Percentage of children cured at day 7 in the intervention group (ePOCT+) as compared to the control group (routine care)

Outcome measure: The child is defined as being cured at day 7 if the caregiver says that the child is cured or has improved since the initial consultation. Non-referred secondary hospitalizations (if caregiver says that child was hospitalized between day 0 and day 7 but the electronic clinical data does not indicate a referral for hospitalization) will however be considered as clinical failures even if the child is already cured at day 7.

Timing and method of measurement: Assessment of subjective clinical cure by the caregiver, and history of non-referred hospitalization will be assessed by telephone or home visit follow-up 7 days (range 6-14 days) after enrollment of the subject. The day of enrollment of the subject is considered as day 0.

Analysis type: Superiority

Secondary consultations:

- % of children with one or more unscheduled re-attendance visits at any health facility by day 7

Timing and method of measurement: Telephone or home visit follow-up 7 days (range 6-14 days) after enrollment of the subject. The day of enrollment of the subject is considered as day 0.

Severe outcome by day 7:

- % of children with non-referred secondary hospitalization by day 7
- % of children who have died by day 7

Timing and method of measurement: Death and non-referred secondary hospitalization will be assessed by telephone or home visit follow-up 7 days (range 6-14 days) after enrollment of the subject. The day of enrollment of the subject is considered as day 0.

Primary referrals:

- % of children referred to hospital or inpatient ward at a health centre at initial consultation

Timing and method of measurement: Documented by the HW at the end of the initial consultation in the eCRF (control arm) or in ePOCT+ (intervention arm) when the subject was enrolled (day 0)

Appropriate case management for malaria at initial consultation

- % of febrile children tested for malaria by RDT and/or microscopy at day 0
- % of malaria positive children (positive RDT result OR positive microscopy result) prescribed an antimalarial at day 0
- % of malaria negative children prescribed an antimalarial at day 0
- % of untested children prescribed an antimalarial at day 0

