Antibiotic prescription is any oral, intramuscular or intravenous (but not topical) antibiotic prescribed by a HCW during the initial consultation or a re-attendance visit.

Antimalarial prescription is any oral, rectal, intramuscular or intravenous antimalarial prescribed by a HCW during the initial consultation or a re-attendance visit.

Febrile child is a child with a history of fever (measured or suspected fever in the past 48 hours) or a high temperature.

Malaria testing is a malaria RDT or microscopy ordered by a HCW during an outpatient visit.

[figure not shown]
3. Methods

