6.1 Analysis methods

Analyses will follow CONSORT guidelines (Campbell, Piaggio, Elbourne, & Altman, 2012; Piaggio et al., 2012; Schulz, Altman, & Moher, 2010; Zwarenstein et al., 2008). Outcomes will be described by arm using summary statistics. Baseline characteristics will be compared by study arm and by cluster study to ensure that the pragmatic allocation of health facilities and sequential rollout of the study did not introduce significant bias. Baseline characteristics which will differ between treatment arms within and over all clusters will be described using summary statistics.

Since the documentation of final treatment in both arms is part of the per protocol definition, only the PP population can be used for primary outcome analysis. The primary outcome will be evaluated using a random effects logistic regression model with the binary outcome variable of antibiotic prescription, with study arm and covariates at patient-level (e.g. age, sex) as fixed effects, and cluster (health facility) and patient included as random effects. Binary secondary outcomes will be evaluated in the same way. All estimates will be reported as odds ratios (ORs) with two-sided 95% confidence intervals (CI). The study will be deemed a success if antibiotic prescription at the initial consultation is 25% less in the ePOCT+ arm compared to the control arm, although we expect a greater reduction based on limited pilot data.

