6.2 Exploratory analyses

Unless specifically described, the following analyses will be analyzed similarly to the binary secondary outcomes, using a random effects logistic regression model with the cluster (health facility) and patient included as a random effect.

- % of children hospitalized among those referred for hospitalization during an initial consultation

Timing and method of measurement: Hospitalization determined by day 7 (6-14) phone call or home visit. Referral for hospitalization as determined by eCRF during the initial consultation.

- % of children referred for malnutrition management during the initial consultation

Timing and method of measurement: Referred for malnutrition as documented in eCRF during the initial consultation.

- % of children referred for or performed at the health facility tuberculosis screening during the initial consultation

Timing and method of measurement: As documented in the eCRF during the initial consultation.

- % of children tested for HIV during the initial consultation:

Timing and method of measurement: As documented in the eCRF during the initial consultation.

- % of children tested for any laboratory test during the initial consultation:

Timing and method of measurement: As documented in the eCRF during the initial consultation

- % of clinicians accepting the ePOCT+ testing, treatment, diagnosis, and management recommendations during the initial consultation

Timing and method of measurement: As documented in the eCRF of the intervention arm (ePOCT+) during the initial consultation

- % of children/caretakers seeking additional medications after the initial consultation

Timing and method of measurement: Asking caretakers if they procured additional medications for their child after the initial consultation by phone call or home visit at day 7 (6-14)

- Change in % of children with antibiotic prescribed over time / across three cluster studies

Timing and method of measurement: Antibiotic prescription as documented in the eCRF (control arm) / ePOCT+ tool (intervention) during the initial visit (day 0).

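### Between-arm odds ratios for antimalarial use among untested and malaria-negative children compare groups formed by a testing decision that ePOCT+ may itself change

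*SAP*

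**What the plan says.** SAP 2.1.2 states that "All secondary outcomes are compared between the intervention (ePOCT+) and control (routine care) arms". Its malaria case-management outcomes include the percentage "of febrile children tested for malaria by RDT and/or microscopy at day 0", the percentage "of malaria negative children prescribed an antimalarial at day 0" and the percentage "of untested children prescribed an antimalarial at day 0". The untested group is not restricted to febrile children.

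The definitions in the same section say that "Malaria testing is a malaria RDT or microscopy ordered by a HCW during an outpatient visit", so test status is fixed during the consultation, after the facility has been allocated. Protocol 3.1 lists among the things ePOCT+ guides the "POC diagnostic tests that should be performed in a given clinical context". Table 2 there gives patients with fever as the target group for the malaria test.

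On analysis, SAP 6.1 says "Binary secondary outcomes will be evaluated in the same way", meaning the random effects logistic model used for the primary outcome, with odds ratios and two-sided 95% confidence intervals. The only relevant adjustment is the general provision in SAP 6.1 for baseline characteristics judged to be imbalanced. The SAP lists no antimalarial outcome over all children or over all febrile children, although Protocol 8.1.6 does foresee determining the percentage of children prescribed an antimalarial.

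**The concern.** The denominators are formed after allocation by a decision that the intervention is built to guide and that the SAP also counts as an outcome. If ePOCT+ leads to more testing of febrile children, those children leave the untested group. What remains is more heavily non-febrile and would seldom receive an antimalarial in either arm. The malaria-negative group gains children whose level of suspicion may differ from those tested under routine care.

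An odds ratio within either group then mixes a change in who is in the group with any change in prescribing. Reported as a between-arm effect under appropriate case management, it could be read as better or worse prescribing when only group membership has moved.

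**Working it through.** The documents give no expected rate, power or testing level for these outcomes, so there is no plan figure to reproduce. The check asks what the planned percentages show when each child's antimalarial decision is the same in both arms and only testing differs. The odds ratios are crude; the planned model adds covariates and random effects.

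**Inputs**
- Anchored to the protocol: 6.0% of febrile children treated (Table 4, Western Province, household survey of under-fives); 1.8% malaria positive (Table 5, Rusizi).
- Assumed: febrile share f = 50% (range 30% to 70%); 0.5% of non-febrile children treated; non-febrile children untested; all positives treated; testing levels as shown.

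**Formulas** (t = share of febrile children tested, q = febrile treated, p = febrile positive, n = non-febrile treated)
- Untested, treated: [f(1−t)q + (1−f)n] / [f(1−t) + (1−f)]
- Negative, treated: (q−p)/(1−p) when testing is unrelated to suspicion
- Any antimalarial, all children: fq + (1−f)n
- Antimalarial without a positive test, all children: fq + (1−f)n − ftp

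**A. Testing unrelated to suspicion, 50% versus 95%**
- Untested, control: (0.015 + 0.0025)/0.75 = 2.33%. ePOCT+: (0.0015 + 0.0025)/0.525 = 0.76%. OR 0.32. Over febrile shares of 30% to 70%, the OR is 0.41 to 0.30.
- At 80% versus 90%: 0.0085/0.60 = 1.42% versus 0.0055/0.55 = 1.00%, OR 0.70. With equal testing, OR 1.00.
- Negative: 0.042/0.982 = 4.28% in both arms, OR 1.00.
- Any antimalarial, all children: 0.030 + 0.0025 = 3.25% in both arms, OR 1.00.
- Without a positive test, all children: 0.0325 − 0.0045 = 2.80% versus 0.0325 − 0.00855 = 2.40%, OR 0.85. This outcome also moves with testing, because testing relabels some treated children as test-positive.

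**B and C. Testing related to suspicion.** Assume 30% of febrile children are high-suspicion (15% treated, 5% positive) and 70% low-suspicion (2.14% treated, 0.4% positive). The averages stay near the anchors: 0.3×15% + 0.7×2.14% = 6.0% and 0.3×5% + 0.7×0.4% = 1.78%. ePOCT+ tests 95% of both groups.

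- **B, control staff test mainly high-suspicion children** (90% and 10%, so 34% overall). Untested, control: [0.5×(0.03×0.15 + 0.63×0.0214) + 0.0025]/0.83 = 1.38%. Negative, control: (0.27×0.10 + 0.07×0.0174)/(0.27×0.95 + 0.07×0.996) = 8.65%.
- **C, control staff often treat high-suspicion children without a test** (30% and 50% tested, so 44% overall). Untested, control: [0.5×(0.21×0.15 + 0.35×0.0214) + 0.0025]/0.78 = 2.82%. Negative, control: (0.09×0.10 + 0.35×0.0174)/(0.09×0.95 + 0.35×0.996) = 3.48%.

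| Scenario (control vs ePOCT+ testing) | Untested, treated | OR | Negative, treated | OR | Any antimalarial, all children |
|---|---|---|---|---|---|
| A: 50% vs 95% | 2.33% vs 0.76% | 0.32 | 4.28% vs 4.28% | 1.00 | 3.25% vs 3.25% |
| B: 34% vs 95% | 1.38% vs 0.76% | 0.55 | 8.65% vs 4.29% | 0.47 | 3.25% vs 3.25% |
| B, smaller gap: 88% vs 95% | 0.85% vs 0.76% | 0.90 | 4.50% vs 4.29% | 0.95 | 3.25% vs 3.25% |
| C: 44% vs 95% | 2.82% vs 0.76% | 0.26 | 3.48% vs 4.29% | 1.25 | 3.25% vs 3.25% |

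**Would restricting to fever, or adjusting for it, be enough?** Only in A, where treatment among untested febrile children is 6.00% in both arms. In B it is 2.72% versus 6.00% (OR 2.28), and in C 6.96% versus 6.00% (OR 0.85).

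**The case against.** The strongest reply is that the testing gap is assumed and could be small. Table 2's footnote treats malaria tests as routinely available, SAP 3.1 gives control staff equivalent clinical training, and Protocol 8.1.4 has them reminded to follow the standard guidelines. Table 2 also allows testing to be confined to a higher-risk febrile sub-group where endemicity is very low, and Table 5 shows under-five malaria prevalence of 0% in Nyamasheke and 1.8% in Rusizi. All of this stands: the size is unknown, and so is the sign of the gap. If ePOCT+ lowered testing from 90% to 80%, scenario A would reverse and the untested odds ratio would be about 1.42. Any gap in either direction still leaves the groups non-comparable.

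Second, these percentages are ordinary process indicators, the protocol lists them as such in 7.1, and the SAP places the testing percentage beside them. That supports keeping them as indicators. It does not support reading their odds ratios as effects of the intervention.

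Third, fewer children treated without a test is a real gain, so a fall in the untested percentage need not be pure artefact. This is right: in practice real and compositional changes would be mixed, and the planned odds ratio cannot separate them.

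Fourth, allocation is not randomised (SAP 3.2), so an all-children denominator does not secure comparability. It removes only the selection introduced after allocation.

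A reader might extend the point to the exploratory percentage "of children hospitalized among those referred for hospitalization during an initial consultation". That does not follow. The protocol describes it as referral completion, which needs referred children as its denominator, and SAP 2.1.2 already compares referral over all children.

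**Conclusion.** The concern holds as a limit on interpretation of two secondary outcomes. When testing of febrile children differs between arms, the planned odds ratios do not compare like with like. For untested children, higher testing under ePOCT+ gave an odds ratio below 1 in every illustration, from about 0.26 to 0.90 in the working above, with no prescription changed. For malaria-negative children it ran from 0.47 to 1.25, so no direction can be stated.

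A reader might infer that the malaria results will show large spurious gains for ePOCT+ in both groups. The documents do not support that. They give no testing rates, contain reasons to expect a small gap, and do not establish that testing will rise. With equal testing the artefact is zero in scenario A. The general baseline adjustment in SAP 6.1 does not settle the matter, because it does not guarantee that fever is included and cannot reach suspicion within febrile children. The primary outcome is unaffected. This is a worthwhile clarification, not a major flaw.

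**What to change.** In SAP 2.1.2, make the between-arm malaria treatment comparisons:

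- (a) any antimalarial prescribed at the initial consultation;
- (b) antimalarial prescribed without a positive malaria test.

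Report each over all initial consultations and over all children with a history of fever, in both arms. State that (b) reflects the combined effect of testing and prescribing, since it moves with testing even when prescribing does not (2.80% versus 2.40% in scenario A). Report (a) with it for that reason.

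Keep the test-conditional percentages as process indicators, shown by arm beside the testing rate and the size of each group, and say in SAP 6.1 that they are not interpreted as intervention effects.

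The cost is SAP wording. Tests, results and treatments are recorded in both arms (SAP 3.1, Protocol 8.1.6), and SAP 5.4 summarises history of fever by arm. The team should confirm that fever history is asked in the same way in both arms, because the fever denominator is neutral only if it is. The downside is that the all-children percentages are smaller and less familiar than the usual indicators, which would still be tabulated.

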	
 
- % of children with ≥1 unscheduled re-attendance visits at any HF by day 7
 
 
Primary referrals:
 
 
- % of children referred to hospital or admitted to inpatient ward at a health center at initial consultation
 
- % of children who were hospitalized among those referred (i.e. referral completed)
 
 
Appropriate case management for malaria at initial consultation:
 
 
- % of suspected cases tested for malaria
 
- % of malaria positive children prescribed an antimalarial
 
- % of malaria negative children prescribed an antimalarial
 
- % of untested children prescribed an antimalarial
 
 
Appropriate case management for other conditions at initial consultation:
 
 
- % of key symptoms and signs checked and diagnostic tests performed by HWs
 
- Distribution of final diagnoses (including their severity) made by HWs
 
- Concordance between treatment prescribed and final diagnoses made by HWs
 
- Concordance between final diagnoses as proposed by ePOCT+ and final diagnoses by HW (intervention HFs only)
 
 
Objective 2: Improve the algorithm and adapt it to spatiotemporal variations
 
 
- Number of positive impact modifications in the algorithm identified by ML analyses
 
- Number of modifications implemented, by type of impact (better clinical cure, less severe clinical outcomes, less medicines or diagnostic tests needed, shorter consultation time)
 
 
Objective 3: Enhance M&E and supportive supervision
 
 
- Number of M&E indicators based on individual data that can be visualized through the medAL-monitor/medAL-outbreak dashboards
 
- Number of supervision and mentorship visits to HFs facilitated by the medAL-monitor tools
 
- Number of HWs reporting having used the medAL-monitor tool for self-auditing their clinical practices
 
- Number of HWs and members of DHMT reporting a positive experience with the medAL-monitor/medAL-outbreak tools
 
 
Objective 4: Create a supportive environment for the use of clinical algorithms and supporting tools
 
 
- Number of sick children attending primary care facilities managed by HWs using the electronic ePOCT+ tool
 
- % of HWs able to assess key clinical signs
 
- Frequency of use of the medAL-monitor/medAL-outbreak tool by district team members
 
- Perception by HWs of the ePOCT+ tool and intervention and the number of improvements they propose for the tool or intervention
 
- Perception by caregivers and community members of the intervention and the number of improvements they propose
 
- Perception by district team members of the medAL-monitor/medAL-outbreak tool and the number of improvements they propose for the tool
 
- Number of medical experts able to modify a clinical algorithm using medAL-creator
 
- Number of computer scientists able to maintain the software and the IT infrastructure for clinical algorithms
 
- Number of data scientists able to analyze clinical data using ML
 
- Patient and provider expenditures related to care of acutely ill children included in the study
 

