- % of children referred to hospital or admitted to inpatient ward at health center at initial consultation
- % of children who were hospitalized among those referred (i.e. referral completed)

*Appropriate case management for malaria at initial consultation*

- % of suspected cases tested for malaria
- % of malaria positive children prescribed an antimalarial
- % of malaria negative children prescribed an antimalarial
- % of untested children prescribed an antimalarial

*Appropriate case management for other conditions at initial consultation*

- % of key symptoms and signs checked and diagnostic tests performed by HWs
- Distribution of final diagnoses (including their severity) made by HWs
- Concordance between final diagnoses made and treatment prescribed by HWs
- Concordance between final diagnoses as proposed by ePOCT+ and final diagnoses by HW (*intervention period only*)

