**Definitions used for the outcome measures and indicators of objective 1**

- Clinical cure is a positive answer to the question “Is the child cured?” OR “Has the child improved?” (if not cured) asked to caregiver through a phone call or SMS (or home visit) at day 7. Non-referred secondary hospitalizations (see definition below) will however be considered as clinical failures even if the child is already cured at day 7.
- Initial consultation is the first visit of a sick child for an acute problem at a HF participating in the study (and thus registered electronically); timeframe from completion of the initial visit up to midnight of the same day.
- Re-attendance visit is a consultation (not necessarily at a HF participating in the study) taking place from the day after initial consultation up to day 7 included. A re-attendance visit can be scheduled (proposed by the HW on a certain day) or unscheduled (upon decision by caregivers).
- Primary referral is a decision of referring the child to hospital taken by the HW at the initial consultation.
- Secondary referral is a decision of referring the child to hospital taken by the HW during a re-attendance visit taking place from the day after initial consultation up to day 7 included.
- Primary hospitalization is an admission to a hospital ward taking place the same day as the initial consultation
- Secondary hospitalization is an admission to a hospital ward taking place from the day after initial consultation up to the phone call at day 7 included. A non-referred secondary hospitalization is a direct visit and admission to a hospital without a re-attendance visit the same day at a HF participating in the study.
- Antibiotic prescription is any oral, intramuscular or intravenous (but not topical) antibiotic prescribed by a HW during the initial consultation or a re-attendance visit.
- Antimalarial prescription is any oral, rectal, intramuscular or intravenous antimalarial prescribed by a HW during the initial consultation or a re-attendance visit.

- Febrile child is a child with a history of fever and/or a high temperature
- Malaria testing is a malaria RDT or microscopy ordered by a HW during an outpatient visit
- Day 7 is a range of 6-14 days post initial consultation to allow for completion of home visit for children whose caregiver reports having no phone / no phone number.

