Timing and method of measurement: Documented by the HW at the end of the initial consultation where the subject was enrolled (day 0)

Definitions:

Clinical cure is a positive answer to the question “Is the child cured?” or if not cured “Has the child improved?” asked to caregiver through a phone call at day 7. Non-referred secondary hospitalizations (see definition below) will be considered as clinical failures even if the child is already cured at day 7.

Clinical failure is a negative answer to the question “Is the child cured?” and “Has the child improved” asked to the caregiver through a phone call at day 7. Non-referred secondary hospitalization (see definition below) will be considered as a clinical failure even if the child is already cured at day 7.

Initial consultation is the first visit of a sick child for an acute problem at a HF participating in the study (and thus registered electronically); timeframe from completion of the initial visit up to midnight of the same day. The initial consultation is considered as day 0.

Re-attendance visit is a consultation (not necessarily at a HF participating in the study) taking place from the day after initial consultation up to day 14 included. A re-attendance visit can be scheduled (proposed by the HW on a certain day) or unscheduled (upon decision by caregivers).

Primary referral is a decision of referring or admitting the child at a hospital or health center for at least one night, taken by the HW at the initial consultation.

Secondary referral is a decision of referring or admitting the child at a hospital or health center taken by the HW during a re-attendance visit taking place from the day after initial consultation up to day 7 included.

Primary hospitalization is an admission to a hospital or health center ward for at least one night taking place the same day as the initial consultation

Secondary hospitalization is an admission to a hospital or health center ward for at least one night taking place from the day after initial consultation up to the phone call at day 7 included. A non-referred secondary hospitalization is a direct visit to hospital without a re-attendance visit the same day at a HF participating in the study. Non-referred secondary hospitalization will be determined if the caregiver reports during the day 7 phone follow-up that the child was hospitalized, even if there was no documentation of a referral from initial and re-attendance visits at participating health facilities.

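### Protocol and SAP define referral and hospitalization differently; under the SAP an own-ward admission counts as both, so hospitalization among those referred does not show who reached hospital

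*SAP*

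**What the plan says.** The definitions at the end of Protocol 7.1 refer to hospitals only and set no minimum length of stay:

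- On referral: "Primary referral is a decision of referring the child to hospital taken by the HW at the initial consultation"
- On hospitalization on day 0: "Primary hospitalization is an admission to a hospital ward taking place the same day as the initial consultation"
- For later hospitalization, up to the day-7 call, the place is again a hospital ward.

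The indicator list in the same section is wider. Under primary referrals it has the percentage "of children referred to hospital or admitted to inpatient ward at health center at initial consultation", and the Synopsis has the same: "of children referred to hospital or admitted to inpatient ward at a health center at initial consultation". A further protocol indicator is the percentage hospitalized among those referred, which the protocol glosses as a completed referral.

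SAP 2.1.2 lists the same composite as the protocol indicator (referral to hospital or to a health centre ward) as a secondary outcome. Its definitions then read:

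- On referral: "Primary referral is a decision of referring or admitting the child at a hospital or health center for at least one night"
- On hospitalization on day 0: "Primary hospitalization is an admission to a hospital or health center ward for at least one night taking place the same day"

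Its definition of secondary hospitalization likewise adds the health centre ward and the one-night minimum.

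SAP 6.2 lists as exploratory the percentage "of children hospitalized among those referred for hospitalization during an initial consultation". The denominator comes from the health worker's electronic entry at the initial consultation. The numerator comes from the day-7 telephone call or home visit.

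**The concern.** SAP 5.2.1 restricts the clusters to health centres and excludes health posts. The category that the SAP adds to both definitions is therefore, where a site has inpatient beds, admission to the enrolling facility's own ward. A decision to admit there is a referral under the SAP, and the admission that follows is a hospitalization. Such a child says nothing about whether a family that was sent elsewhere arrived, yet belongs in the denominator and can enter the numerator of the analysis meant to show that.

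Three results are exposed: the exploratory completion proportion, the interpretation of the secondary primary-referral outcome, and the count of clinical failures at day 7. Facilities are not randomized and arms are split geographically (SAP 3.2). Inpatient practice may therefore differ between arms for reasons unrelated to ePOCT+, and the baseline facility characteristics in SAP 5.4 do not name inpatient capacity.

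**Working it through.** The plan gives no figure to reproduce here, so the check is a comparison of text followed by an illustration on stated assumptions.

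**1. The definitions side by side**

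| Term | Protocol 7.1, definition | Protocol 7.1 and Synopsis, indicator | SAP 2.1.2, outcome list | SAP 2.1.2, definition |
|---|---|---|---|---|
| Primary referral | hospital only | hospital or health centre ward | hospital or health centre ward | hospital or health centre, at least one night |
| Primary hospitalization | hospital ward, no minimum | not listed | not listed | hospital or health centre ward, at least one night |
| Secondary hospitalization | hospital ward, no minimum | only the non-referred subset is listed | only the non-referred subset is listed | hospital or health centre ward, at least one night |

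For referral, three of the four entries agree on hospital or health centre ward in their scope of facility. The outlier is the protocol's own definition, so that conflict starts inside the protocol. The SAP's one-night condition is the only further difference. For hospitalization the protocol names hospitals only, and the SAP departs from it on both place and minimum stay.

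**2. The overlap**

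Take a child admitted overnight on day 0 to the ward of the health centre that enrolled them. Under the SAP definitions this is a primary referral and a primary hospitalization. Under the protocol definitions it is neither.

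**3. Effect on the completion proportion**

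Assumed inputs, none given in the documents:

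- q: share of SAP referrals that are own-ward admissions
- r: probability that the caregiver reports such a stay as hospitalization at the day-7 contact
- c: true completion among children referred to hospital

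Proportion = q×r + (1−q)×c. The shift from the true value is q×r + (1−q)×c − c = q×(r−c), which is positive only when r > c.

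With c = 60%:

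| q | r = 100% | r = 90% | r = 70% |
|---|---|---|---|
| 25% | 70% | 67.5% | 62.5% |
| 50% | 80% | 75% | 65% |
| 75% | 90% | 82.5% | 67.5% |

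For q = 50% and r = 70%: 0.5×0.7 + 0.5×0.6 = 0.65.

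Over c from 40% to 80%, q from 25% to 75% and r from 70% to 100%, the shift runs from 0.75×(0.7−0.8) = −7.5 points to 0.75×(1.0−0.4) = +45 points.

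Between arms with equal c = 60% but q = 25% against 50%, the spurious difference is 0.25×(r−0.6): 10 points at r = 100% and 2.5 points at r = 70%.

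**4. The composite referral outcome**

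Protocol 3.1 says ePOCT+ is to guide the decision to refer urgently to a higher level of care. If hospital referral were 2% in control and 3% in intervention, and ward admission 2% and 1% (hypothetical), the composite would be 2% + 2% = 4% against 3% + 1% = 4%.

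**5. Day-7 cure**

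A non-referred secondary hospitalization overrides a report of cure. SAP 2.1.2 lets secondary hospitalization include a health centre ward, but describes the non-referred subset as presenting directly to hospital. The outcome text in the same section relies instead on a caregiver report of hospitalization with no referral in the electronic data, and names no place. A later ward stay at a health centre is a failure on one reading and not on another. It is also unstated whether an own-ward admission recorded on day 0 is the kind of referral that exempts a child from failure. SAP 6.1 expects about 3% not cured. If the rule moved 0.3 points of children (assumed), that would be 0.3/3 = one tenth of failures.

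**The case against.** The strongest reply has four parts.

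First, the referral outcome as listed is the same in both documents, and the SAP definition can be read as bringing the protocol's definition into line with the protocol's own indicator. This stands. A reader might infer from the definitions alone that the protocol confines its referral outcome to hospitals; its indicator list and Synopsis show otherwise.

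Second, a reader might infer that own-ward admissions are automatically counted as completed referrals. The documents do not support that. SAP 6.2 takes hospitalization from the day-7 contact, so the child counts only if the caregiver is reached and describes the stay as hospitalization. SAP 6.1 cites telephone losses of 13–25% in previous studies. SAP 6.2 also drops the protocol's completed-referral gloss. What remains is overlap by definition, plus a figure that depends on how caregivers understand the question.

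Third, any composite can hide opposite movements, and neither document says this one measures onward referral. That is fair: the 4% against 4% example is a reason to report components, not evidence of an error.

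Fourth, place of referral or admission may already be captured in the case report forms, which are not available for this review. If so, the fix needs wording only.

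**Conclusion.** The point holds in a limited form. The protocol needs to reconcile its referral definition with its referral indicator, and the two documents need to reconcile their hospitalization definitions. As the SAP stands, the proportion hospitalized among those referred mixes children sent to hospital with children who were never sent anywhere, so it cannot be read as referral completion.

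The size is unknown because q, r and c are all assumed. The bias could be negligible if few sites admit overnight, large if many do and caregivers report it, or downward if r is below c. A claim that completion is always inflated, or most inflated in the arm that admits more in-house, would go beyond the documents, since both need r to exceed c.

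The ambiguity about later ward stays reaches the day-7 cure outcome, which is secondary. The completion analysis is exploratory in the SAP and a secondary indicator in the protocol. The primary outcome, antibiotic prescription at the initial consultation, is untouched. The correction is worth making before analysis but does not threaten the trial's main conclusion.

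**What to change.** - Use one set of referral and hospitalization definitions in Protocol 7.1 and SAP 2.1.2, stating for each term whether health centre wards count and whether the one-night minimum applies.
- Keep the composite primary-referral outcome, and report referral to hospital and admission to a health centre ward separately beside it, by arm.
- Compute completion only among children referred to hospital, with hospital admission as the numerator.
- State whether a health centre ward stay can be a non-referred secondary hospitalization, and so a clinical failure, and whether a day-0 own-ward admission counts as a referral for that rule.

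The cost is mainly wording. Each component is rarer than the composite, so its estimate will be less precise. The referral decision is already recorded in both arms (Protocol 8.1.6); place of admission has to be noted at the day-7 contact if it is not already.
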